# 5.4.1.3.7. Acetaminophen/Paracetamol (rescue medication)

Acetaminophen/paracetamol will be issued by the study sites in its approved marketed product dress, (carton, bottle, documents). Any approved commercial product of acetaminophen/paracetamol tablet/caplet/capsule is permitted.

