## 5.9. Rescue Therapy

Acetaminophen/paracetamol will be issued to the subject by the study sites in its approved marketed product dress, (carton, bottle, documents) for use as rescue medication.

During the Washout period and the Initial Pain Assessment Period, subjects may take rescue medication (acetaminophen/paracetamol) as needed for osteoarthritis or other types of pain or illness up to a maximum daily dose of 3000 mg/day. Rescue medication must be discontinued at least 24 hours prior to the Baseline (Day 1) visit.

In the event of inadequate pain relief for osteoarthritis during the Double-blind Treatment period (between the Baseline [Day 1] visit and Week 16), subjects may take up to a maximum permitted daily dose of 3000 mg but only up to 3 days per week.

From the Baseline (Day 1) visit through Week 16 visit, subjects taking rescue medication greater than 3 days per week (any level of acetaminophen/paracetamol used specifically for osteoarthritis pain) must be interviewed by study site personnel to determine if this is due to lack of efficacy or other reasons, and the discussion should be noted in the subject's source documents. Subjects who have taken rescue medication more frequently than specified in the protocol during the treatment period due to lack of efficacy and indicate that they cannot or will not follow the rescue medication protocol requirements because of insufficient osteoarthritis pain relief should be withdrawn from investigational product due to lack of efficacy and entered in the Early Termination Follow-up period (refer to Section 6.4). Subjects who indicate that they anticipate being able to take rescue medication no more than 3 days per week going forward will be allowed to continue in the treatment period. However, if these subjects continue to take rescue medication more than 3 days per week, they should be withdrawn from investigational product and entered into the Early Termination Follow-up period (refer to Section 6.4).

Between the Week 16 and Week 64 visits, subjects may take acetaminophen / paracetamol rescue medication daily, up to the maximum permitted dose of 3000 mg per day. After the Week 64 visit, subjects may be started on standard of care treatments for osteoarthritis pain. Subjects may continue to use acetaminophen as needed up to the maximal permitted dose of acetaminophen per day as permitted by local or national labeling.

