The incidence and number of days per week of rescue medication use will be analyzed for Weeks 2, 4, 8, 16, 24, 32, 40, 48 and 56, and the amount of rescue medication use per week will be analyzed for Weeks 2, 4, 8 and 16. The incidence of use of rescue medication will be analyzed using logistic regression for binary data, with model terms for Baseline WOMAC Pain subscale score, Baseline Diary Average Pain, index joint, Kellgren-Lawrence grade, NSAID group and treatment group. The number of days and amount of rescue medication (mg dosage of acetaminophen) will be analyzed using the Negative Binomial model, with model terms of Baseline WOMAC Pain subscale score, Baseline WOMAC Pain subscale score, Baseline Diary Average Pain, index joint, Kellgren-Lawrence grade, NSAID cohort, and treatment group. Estimated levels of rescue medication use will be shown for each treatment group, and the ratio (with 95% CI) for comparisons versus NSAID will be shown. Imputation for missing rescue medication use will be summarized up to Week 64, and the amount of rescue medication taken in a week summarized up to Week 16.

The incidence of and time to withdrawal due to lack of efficacy will also be analyzed for discontinuation up to Week 56 (end of treatment period). The time to discontinuation will be analyzed using the log-rank test, with Kaplan-Meier estimates of the time to discontinuation shown for selected percentiles, dependent on the level of discontinuation. The expectation is that these would be the 1st, 2nd, 5th, 10th and 25th percentiles. Other percentiles may be shown if the level of discontinuation due to lack of efficacy as calculated using Kaplan-Meier procedure is sufficiently large. The analysis of the incidence of discontinuation due to lack of efficacy will be made using logistic regression for binary data, with model terms for baseline WOMAC Pain subscale score, Baseline Diary Average Pain, index joint, Kellgren-Lawrence grade, NSAID group and treatment group.

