- *Work Productivity and Activity Impairment Questionnaire for Osteoarthritis (WPAI:OA) impairment scores change from Baseline to Weeks 16, 24, 56 and 64.*
- *EuroQol 5 Dimension (EQ-5D-5L™) dimensions and overall health utility score at Baseline and Weeks 8, 16, 24, 40, 56 and 64.*
- *Treatment Satisfaction Questionnaire Medicine v.II (TSQM v.II) satisfaction with effectiveness, side effects and convenience, and overall satisfaction at Weeks 16 and 56.*
- *Patient Reported Treatment Impact Assessment-Modified (mPRTI) at Weeks 16 and 56.*
- *Incidence and Time to discontinuation due to Lack of Efficacy.*
- *Usage of rescue medication (incidence and number of days of use) during Weeks 2, 4, 8, 16, 24, 32, 40, 48, 56 and Week 64.*
- *Usage of rescue medication (amount taken) during Weeks 2, 4, 8 and Week 16.*
- *Health Care Resource Utilization at Baseline and Weeks 64, and 80.*

Note, in this document where reference is made to three co-primary efficacy endpoints this relates to all countries except Japan, where there are only two co-primary efficacy endpoints (WOMAC Pain and Physical Function subscale scores).

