8.1.2. Analyses for Categorical Data

The number of days and amount (mg of acetaminophen/paracetamol) of rescue medication used per week will be analyzed using a negative binomial model with model terms of treatment group and covariates as described in [Section 6.4](#). In this model the error term is defined with a negative binomial distribution, and 'log' is used as the link function. Output from this analysis will be the estimated number/amount of rescue medication use per week in each treatment group, and (following the exponential back transformation) the ratio of rescue medication use for the treatment comparisons shown in [Section 4.1](#). The 95% CIs will be given for the estimates of both the individual treatment groups and the treatment group ratios.

The change from Baseline in the NIS will be analyzed using a Cochran-Mantel-Haenszel (CMH) test for 'row mean scores differ', using change from Baseline categories as the scores in the analysis, and stratified by the combined levels of the three stratification factors ([Section 6.4](#)). Output will show number and percentage of subjects whose NIS score worsened (change >0), improved (change <0) or had no change, in addition to the mean (with standard deviation) and median change, and minimum and maximum change. This analysis will be performed for the two treatment comparisons separately, and shown by visit and worst change (largest change from baseline to any post-baseline visit), and by last change (summary statistics only).

090017764931781b656\Approved\Approved On: 03-Oct-2019 08:56 (GMT)

The change from Baseline in the Patient's Global Assessment of Osteoarthritis to Weeks 2, 4, 8, 16, 24, 32, 40, 48, and 56 will also be analyzed using the CMH test and stratified by the combined levels of the stratification factors. Changes by each level of improvement will be summarized, as well as any improvement (change<0), and any worsening (change>0). For this analysis imputation for missing data will use mixed BOCF/LOCF, BOCF, and LOCF.

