Incidence of treatment discontinuation due to lack of efficacy (up to Week 56/End of Treatment)	ITT	Logistic Regression	BL WOMAC Pain, BL Diary Average Pain, Index Joint (Knee/Hip), Highest KL grade (2, 3 or 4), NSAID cohort, Treatment Group	Observed	Secondary Endpoint Analysis

090017764931816561 Approved On: 08-10-2019 08:56 (GMT)

Incidence of rescue medication use during Weeks 2, 4, 8, 16, 24, 32, 40, 48, and 56	ITT	Logistic Regression	BL WOMAC Pain, BL Diary Average Pain, Index Joint (Knee/Hip), Highest KL grade (2, 3 or 4), NSAID cohort, Treatment Group	LOCF	Secondary Endpoint Analysis
Number of days of rescue medication use during Weeks 2, 4, 8, 16, 24, 32, 40, 48, and 56	ITT	Negative Binomial	BL WOMAC Pain, BL Diary Average Pain, Index Joint (Knee/Hip), Highest KL grade (2, 3 or 4), NSAID cohort, Treatment Group	LOCF	Secondary Endpoint Analysis
Amount (mg) of rescue medication taken during Weeks 2, 4, 8 and 16	ITT	Negative Binomial	BL WOMAC Pain, BL Diary Average Pain, Index Joint (Knee/Hip), Highest KL grade (2, 3 or 4), NSAID cohort, Treatment Group	LOCF	Secondary Endpoint Analysis
EQ-5D-5L dimensions (Mobility; Self-care; Usual activity; Pain/Discomfort; Anxiety/Depression) and Overall Health Utility at Baseline and Weeks 16, 24 and 56	ITT	Summary	NA	Observed	Secondary Endpoint Analysis
EQ-VAS at Baseline and Weeks 16, 24 and 56	ITT	Summary	NA	Observed	Secondary Endpoint Analysis
mPRTI endpoints (willingness to re-use; patient preference) at Weeks 16 and 56	ITT	CMH test	Treatment group [1]	Observed	Secondary Endpoint Analysis
TSQM endpoints (satisfaction with effectiveness, side effects and convenience, and overall satisfaction) at Weeks 16 and 56	ITT	ANCOVA	BL Diary Average Pain, Index Joint (Knee/Hip), Highest KL grade (2, 3 or 4), NSAID cohort, Treatment Group (Study site as a random effect)	Observed	Secondary Endpoint Analysis
WPAI endpoints (% work time missed; % impairment while working; % overall work impairment; % activity impairment) at Weeks 16, 24 and 56	ITT	ANCOVA	BL Score, BL Diary Average Pain, Index Joint (Knee/Hip), Highest KL grade (2, 3 or 4), NSAID cohort, Treatment Group (Study site as a random effect)	Observed	Secondary Endpoint Analysis
Healthcare Resource Utilization at baseline, weeks 56 and 64	ITT	Descriptive Summary	Treatment group	Observed	Secondary Endpoint Analysis

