Using the Week 2 interval described above for a subject, ie, study days [8-14], we have the following rescue medication example data.

The amount taken and number of days of rescue medication use is adjusted for the duration of the Weekly interval.

09001776e1931781b6561ApprovedApproved On: 03-10-2019 08:56 (GMT)

Study Day (Week)	Number of Doses of RM taken [1]	Number of Doses of RM taken [1] with LOCF imputation
8 (Week 2)	2	2
9 (Week 2)	Missing	2 [2]
10 (Week 2)	0	0
11 (Week 2)	1	1
12 (Week 2)	Missing	1 [2]
13 (Week 2)	2	2
14 (Week 2)	0	0

[1] 500mg tablets of acetaminophen; [2] Using LOCF imputation for missing data

For this subject the following data will be calculated for Week 2:

- Incidence of rescue medication taken in Week 2: Yes. Rescue medication taken on days 8, 9 (imputed), 11, 12 (imputed), 13.
- Number of days of rescue medication use in Week 2: 5. For days 8-14 we have rescue medication taken on days 8, 9 (imputed), 11, 12 (imputed), and 13. The number of days taken for the 7 day period is $5/7*7=5$.
- Amount (mg) of rescue medication use in Week 2: For days 8-14 we have the number of doses taken of 2, 2 (imputed), 0, 1, 1 (imputed), 2, and 0. The number of doses taken for the 7 day period is $8/7*7=8$, making the amount of acetaminophen dosage of 4000mg.

Example of calculating rescue medication data from Daily Diary Data (Subject discontinues)

In this example, a subject discontinues on study day 62, a few days after a Week 8 visit (which was on study day 60). The Week 5-8 data is calculated as described above (eg, Week 8 using days [50, 56]). The subject has rescue medication data as shown below.

09001776e1931781b6561Approved\Approved On: 08-10-2019 08:56 (GMT)

Study Day (Week)	Number of Doses of RM taken [1]	Number of Doses of RM taken [1] with LOCF imputation
57 (Week 9)	1	1
58 (Week 9)	1	1
59 (Week 9)	Missing	1 [2]
60 (Week 9)	Missing	1 [2]
61 (Week 9)	Missing	1 [2]
62 (Week 9)	Missing	1 [2]
63 (Week 9)	Missing	1 [2]

[1] 500mg tablets of acetaminophen; [2] Using LOCF imputation for missing data

Week 9 is calculated as days 57 to 63. The data up to the end of the last week the subject was in the trial is imputed using LOCF as shown above. Therefore the Week 9 scores are then used to impute the Weekly data for summary and analysis for Weeks 10 to 56 (up to Week 16 for the amount of rescue medication use).

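### Weekly rescue amount is modelled in milligrams with a negative binomial and no robust variance, so its standard errors depend on the unit and are usually too large when many subjects take none

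*SAP*

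**What the plan says.** SAP 8.1.2 sets the model: "The number of days and amount (mg of acetaminophen/paracetamol) of rescue medication used per week will be analyzed using a negative binomial model". It adds: "In this model the error term is defined with a negative binomial distribution, and 'log' is used as the link function". The output is an estimated level per group and a ratio for each tanezumab dose against NSAID, with 95% confidence intervals. SAP 8.2.2 item 5 repeats the model with its covariates. Protocol 9.2.2 agrees: "The number of days and amount of rescue medication (mg dosage of acetaminophen) will be analyzed using the Negative Binomial model".

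Neither document names a robust variance, a scale parameter, a two-part model or a check of fit for this outcome.

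The amount endpoint is limited to four time points. SAP 6.1 lists "Usage of rescue medication (amount taken) during Weeks 2, 4, 8 and Week 16", and the table in SAP 8.2.5 has "Amount (mg) of rescue medication taken during Weeks 2, 4, 8 and 16".

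The outcome is zero or a multiple of the tablet strength. The worked examples in the SAP appendix on rescue medication use 500 mg tablets. Strength is not fixed, however. Protocol 5.4.1.3.7 says: "Any approved commercial product of acetaminophen/paracetamol tablet/caplet/capsule is permitted". Protocol 7.1.2 has the strength recorded. Protocol 5.9 limits use between Baseline and Week 16: "subjects may take up to a maximum permitted daily dose of 3000 mg but only up to 3 days per week".

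Two other rescue endpoints run to Week 56: incidence by logistic regression (SAP 8.1.3 and 8.2.2 item 3), and number of days by the same negative binomial model. SAP 4.2 makes no multiplicity adjustment for secondary endpoints of this kind.

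**The concern.** A negative binomial is a model for counts. Weekly milligrams are not a count: they are zeros plus values that jump in steps of several hundred. The model ties the variance and the probability of zero to the same mean and dispersion. Changing the unit therefore changes the fitted dispersion, and the model-based standard error changes with it. A p-value should not depend on whether the dose is written in mg, grams or tablets.

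The practical risk is a test of amount that can hardly ever reach significance. SAP 8 includes efficacy data whether or not rescue was taken, so readers will look at rescue use when they interpret the WOMAC results. Week 16 is both the primary efficacy time point and one of the four affected. Amount is also the only rescue endpoint that measures dose.

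**Working it through.** The documents give no standard error, dispersion, mean or share of non-users for rescue use, so there is no precision figure to reproduce. The SAP's own mg arithmetic is correct: 2+2+0+1+1+2+0 = 8 doses, 8 × 500 = 4000 mg; and 7 × 500 = 3500 mg.

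**Step 1: why the unit matters.** Take two groups of n subjects with means m0 and m1, variances s0² and s1², and no covariates.

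- Negative binomial variance: μ + kμ². Probability of zero: (1 + kμ)^(−1/k).
- Estimate: log(m1/m0).
- Model SE² = (1/m0 + k)/n + (1/m1 + k)/n.
- Robust SE² = s0²/(n·m0²) + s1²/(n·m1²).

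Multiply every value by 500. The estimate and the robust SE do not change. In the model SE, 1/m almost vanishes and k is re-estimated. The same share of zeros must now be fitted at a mean 500 times larger, so k rises.

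**Step 2: one data set in both units.** From protocol section 3: 1000 per arm. Assumed: 50% v 40% users, with mixed use of 1 to 7 days at 1, 2, 4 or 6 tablets of 500 mg per day.

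| | Tablets | mg |
|---|---|---|
| k | 3.86 | 14.10 |
| Log ratio (ratio) | −0.169 (0.84) | −0.169 (0.84) |
| Model SE | 0.0923 | 0.1679 |
| Model 95% CI for ratio; p | 0.70 to 1.01; 0.067 | 0.61 to 1.17; 0.31 |
| Robust SE | 0.0837 | 0.0837 |
| Robust 95% CI; p | 0.717 to 0.995; 0.043 | 0.717 to 0.995; 0.043 |

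Hand check in mg: √(2 × 14.10/1000) = 0.168. The robust SE implies an average squared coefficient of variation of 0.0837² × 1000/2 = 3.50, so k is 14.10/3.50 ≈ 4.0 times what the spread requires, and √4.0 = 2.0 = 0.1679/0.0837.

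The reason is the zeros. The mean mg in this pattern is about 1447 at 50% users and 1155 at 40%, average 1301. With k = 3.50 the model would predict (1 + 3.5 × 1301)^(−1/3.5) = 9% zeros, against about 55% expected. With k = 14.1 it predicts 50%.

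**Step 3: range of model SE / robust SE in mg.** All use patterns are assumptions. The user share is the same in both arms.

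| Use among users | 40%, 50%, 60% users | 90% users |
|---|---|---|
| Fairly even (1 to 3 days, 2 tablets) | 2.86, 2.81, 2.77 | 2.18 |
| Mixed | 1.98, 1.91, 1.79 | 1.23 |
| Heavy-tailed | 1.75, 1.65, 1.56 | 1.05 |

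A pattern kept inside the protocol 5.9 limit, with 20% fewer users in the tanezumab arm, gave 2.7 at 50% control-arm users and 2.3 at 90%. With no zeros the ratio is about 0.8 to 1.1, and lower still with the heaviest tail. In tablets it runs from about 0.8 to 1.6, so tablets are not a safe unit either.

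**Step 4: rejection rates at two-sided 5%, 300 runs per pattern.**

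| Pattern (50% v 40% users) | mg model | Tablet model | Robust |
|---|---|---|---|
| Fairly even | 5% | 91% | 98% |
| Mixed | 14% | 66% | 72% |
| Heavy-tailed | 16% | 66% | 62% |

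With no true difference, the mg model rejected in 0 of 300 runs in each pattern. Robust errors rejected in 3% to 7%, with a simulation error of √(0.05 × 0.95/300) = 1.3 percentage points.

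**Step 5: the parallel endpoints.** With 50% v 42% users (a 16% reduction), the mg model reached p<0.05 in 1% to 5% of trials and the days model in 71% to 85%. A comparison of proportions, standing in for the logistic model, did so in 95% to 97%. For days, model SE / robust SE was about 1.0 to 1.4 when there were non-users.

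**Limits.** The simulations had no covariates and no LOCF. With the plan's covariates the fitting weights, μ/(1 + kμ), also depend on the unit, so the ratio itself is then nearly rather than exactly the same in both units.

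**The case against.** The strongest reply is that little is lost. Rescue use is also analysed by incidence and by days. A difference that comes from fewer users would usually show there, and only a difference confined to dose per user would rest on amount alone. The endpoint is secondary, the ratio itself is still reported, and the error usually widens intervals, so it does not create false claims. No primary or key secondary result moves. All of this stands, and it sets the severity.

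It is also fair to say that a model-based variance is inferred from silence. It remains the natural reading, because the SAP defines the error distribution and names no other variance.

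Four stronger readings are tempting, and the documents do not support them:

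- That the standard error is more than twice too large. This depends on the share of non-users and the spread among users, which are not given. Plausible inputs lie on both sides of two.
- That a real difference in rescue use would go unseen. Step 5 shows otherwise for differences driven by fewer users.
- That days per week has the same fault. Days has no arbitrary unit and is only mildly affected.
- That rescue use is the main check on the WOMAC results. Neither document says so. Acetaminophen influence is also addressed by the 24-hour abstention before efficacy visits, the limit on days per week to Week 16 (both protocol 5.9), and the per-protocol exclusion in SAP 5.6.2.

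**Conclusion.** The point holds for rescue amount in mg at Weeks 2, 4, 8 and 16. As written, the confidence intervals and p-values for that endpoint depend on the unit and do not reflect the spread in the data.

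The unit dependence follows from the model and needs no assumed rate. The size does need assumptions: roughly 1.6 to 2.9 times too large at about half non-users, about 1.05 to 2.3 times at 10% non-users, and about 0.8 to 1.1 times with no zeros. The upper figure of 2.3 comes from a case with 10% non-users in the control arm only. The direction is usually conservative. The likely harm is a false statement of no difference in amount, possibly beside significant results for incidence and days. Severity is minor: one secondary endpoint without multiplicity control.

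**What to change.** In SAP 8.1.2 and 8.2.2 item 5, keep the log-link mean model and its covariates. Add one sentence before unblinding: standard errors, confidence intervals and p-values for rescue amount, and for consistency number of days, will use the empirical (sandwich) variance.

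The amount can then stay in mg. Switching to tablets alone is not enough, because product strength is not fixed and the tablet standard errors are also off. If exact unit independence is wanted with covariates in the model, a Poisson-type log-link estimating equation with sandwich variance gives it.

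The cost is one SAP sentence and one program option. Data collection and the estimand do not change. Protocol section 9 lets the SAP modify planned analyses and asks for an amendment only for major changes to the primary endpoint or its analysis, so none appears necessary.
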